5.3.3. Covariates

The list of demographic and clinical characteristics that will be used to describe the cohort and considered for inclusion as covariates in models are provided in Table 5.3. Age, sex, state of residence and prior COVID-19 vaccinations will be obtained from the HealthVerity claims database and state vaccine registries. The HealthVerity claims database will be the sole source of all other variables.

All covariates will be assessed on or prior to index date and will therefore be considered as time-fixed variables during the follow-up. Categories may be collapsed or covariates may be excluded or combined if models fail to converge or if patient counts are low (Section 5.7.2). Additionally, categories with large patient counts may be split further.

Table 5.3 Demographic and Clinical Characteristics

Variable	Role(s)	Operational definition
Age	-Inclusion/ exclusion	Age assessed at index date.
	criteria	Categorized as: 18-49, 50-64 or 65+ years.
	-Descriptive	
	(continuous and	
	categorical)	
	-Covariate	
	(categorical)	
	-Subgroup	
	(categorical)	
Sex	-Inclusion/ exclusion	Sex assessed at index date.
	criteria	Male, female or unknown.
	-Descriptive	
	-Covariate	
State of residence	-Inclusion/ exclusion	Defined in Section 5.2
	criteria	California or Louisiana
	-Descriptive	
	-Covariate	
	-Subgroup	
Payor	-Descriptive	Payor assessed at index date.
	-Covariate	Commercial, Medicaid, Medicare Advantage,
		Unknown, Missing

Variable	Role(s)	Operational definition
CDC-defined high	-Descriptive (any	Assessed in the year prior to index
risk for severe	high-risk condition	• Age ≥ 50 years
COVID-19 ²	and for each	Asthma
	individual condition)	Cancer, as hematologic malignancies
	-Covariate (each	Cerebrovascular disease
	individual condition except age ≥ 50 years)	Chronic kidney disease: people receiving dialysis
		Chronic lung diseases: bronchiectasis,
		COPD, interstitial lung disease, pulmonary
		embolism, pulmonary hypertensionChronic liver diseases: cirrhosis, non-
		alcoholic fatty liver disease, alcoholic liver
		disease, autoimmune hepatitis
		Cystic fibrosis
		Diabetes mellitus, type 1
		Diabetes mellitus, type 2
		Disabilities, including Down syndrome
		Heart conditions: heart failure, coronary
		artery disease, or cardiomyopathiesHIV
		Mental health conditions: mood disorders
		including depression; Schizophrenia
		spectrum disorders
		Neurologic conditions limited to dementia
		Obesity (BMI ≥30 kg/m²)
		Primary immunodeficiencies
		Smoking, current and former
		Solid organ or blood stem transplantation
		Tuberculosis
		Use of corticosteroids or other
		immunosuppressive medications
		The lists of codes are provided in the Protocol
		Annex. Note: due to limitations of claims data,
		"physical inactivity" will not be measurable
		and has been removed from the list.

Variable	Role(s)	Operational definition
Charlson-Deyo	-Descriptive	Assessed in the year prior to index
Comorbidity	(continuous and	Conditions are scored as:
Index ³	categorical)	1 point for each of:
	-Covariate	Myocardial infarction
	(categorical)	• CHF
		Peripheral vascular disease
		Cerebrovascular disease
		Dementia
		Chronic pulmonary disease
		Connective tissue disease
		Peptic ulcer disease
		Mild liver disease
		Diabetes mellitus without chronic
		complications
		2 points for each of:
		Hemiplegia
		Moderate to severe renal disease
		Diabetes with chronic complications
		Cancer, including leukemia and lymphoma
		3 points for moderate or severe liver disease
		6 points for each of:
		Metastatic carcinoma
		• HIV/AIDS
		Categorized as: 0, 1 or 2+
		The list of codes is provided in the Protocol
		Annex
Receipt of skilled	-Descriptive	Assessed in the year prior to index date
nursing care	-Covariate	Yes or No
and/or long-term		The list of codes is provided in the Protocol
care facility stay in		Annex
year prior to index		
Wellness visit	-Descriptive	Assessed in the year prior to index date
	-Covariate	Yes or No
		The list of codes is provided in the Protocol
D 1	D :::	Annex
Decreased	-Descriptive	Assessed in the year prior to index date
functional status	-Covariate	Yes or No The list of codes is appriited in the Protocol
		The list of codes is provided in the Protocol
		Annex

Variable	Role(s)	Operational definition
Influenza	-Descriptive	Assessed in the year prior to index
vaccination in year	-Covariate	Yes or No
prior to index		The list of codes is provided in the Protocol
		Annex
Pneumococcal	-Descriptive	Assessed in the year prior to index
vaccination using	-Covariate	Yes or No
all-available time		The list of codes is provided in the Protocol
prior to index		Annex
Herpes zoster	-Descriptive	Assessed in the year prior to index
vaccination using	-Covariate	Yes or No
all-available time		The list of codes is provided in the Protocol
prior to index		Annex
Outpatient visits	-Descriptive	Number of outpatient visits in 365 days prior
prior to index	(continuous and	to index
	categorical)	Categorized as: 0, 1 or 2+
	-Covariate	The list of codes is provided in the Protocol
	(categorical)	Annex, and includes office/clinic visits as well
		as telehealth.
Inpatient	-Descriptive	Number of inpatient admissions in 365 days
admissions prior to	(continuous and	prior to index
index	categorical)	Categorized as: 0, 1 or 2+
	-Covariate	The list of codes is provided in the Protocol
Г	(categorical)	Annex
Emergency	-Descriptive	Number of emergency department visits in
department visits	(continuous and	365 days prior to index
prior to index	categorical) -Covariate	Categorized as: 0, 1 or 2+
		The list of codes is provided in the Protocol Annex
Telehealth visits	(categorical) -Descriptive	Number of telehealth encounters (CPT:
prior to index	(continuous and	99201-99215) in 365 days prior to index
prior to macx	categorical)	Categorized as: 0, 1 or 2+
	-Covariate	Categorized as. 0, 1 of 2
	(categorical)	
Number of	-Descriptive	Number of visits in any setting with CPT in
documented	(continuous and	365 days prior to index: 86408, 86409, 0225U,
SARS-CoV-2 tests	categorical)	0226U
in the 180 days	-Covariate	Categorized as: 0, 1 or 2+
prior to index	(categorical)	
Prior post-	-Descriptive	Assessed in the year prior to index, any
COVID-19	-Covariate	encounter regardless of setting with ICD-10-
conditions		CM U09.9 "Post-COVID-19 condition"
		Yes or No

Variable	Role(s)	Operational definition
Prior COVID-19	-Descriptive	Any encounter with ICD-10-CM code: U07.1
diagnosis	-Covariate	between 90 and 365 days prior to index
		Yes or No
Prior bivalent	-Descriptive	Where the BNT162b2 XBB.1.5 vaccine is the
BA.4/5 COVID-19	-Subgroup	exposure of interest. Using all-available
vaccine		lookback data, received bivalent BA.4/5
		COVID-19 vaccine (regardless of brand) prior
		to index
		Yes or No
		The list of codes is provided in the Protocol

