- A key assumption of the TND is that exposure (here, COVID-19 vaccination) does not impact the probability of selection in the case (a positive test result on a COVID-19 test) or control population (a negative test result on a COVID-19 test). It is possible that vaccinated persons may be less likely to be seek testing in order to become a case than unvaccinated persons. This, if present, would create collider stratification bias via the requirement for testing in a TND, which biases estimates away from the null and may lead to overestimations of VE. 12-14
- Owing to the case-control nature of the design, TND allows for estimation of odds ratios (OR) but not hazard or risk ratios. OR are not directly interpretable as percentage reduction in risk, which is an easily interpretable summary measure of VE. OR with a protective direction of effect (ratio < 1) will underestimate risk, leading to underestimations of VE. 15 A cohort design allows for absolute estimates of risk such as risk differences.

The use of a retrospective cohort study allows for the adoption of design principles of randomized control trials to help mitigate some of these biases.

Cohort identification will begin from the date of EUA or FDA approval for the BNT162b2 formulation. Study follow-up will occur from FDA EUA or approval date until COVID-19 diagnosis or other outcome of interest (hospitalization, emergency department visit, outpatient encounter, end of medical and/or pharmacy enrollment, or death [according to the mortality database]).

In aims 1, 2 and 4, vaccination status will be measured as a time-varying exposure. In aims 3 and 5, vaccination status will be measured as a time-fixed exposure. Exposed person-time begins 14 days after receipt of a BNT162b2 formulation. Unexposed person-time is unvaccinated person-time, as well as 0-13 days after vaccination. The unexposed group will be further stratified by previous vaccination status for relative VE: XBB.1.5 unvaccinated and BA.4/5 vaccinated; XBB.1.5 and BA.4/5 unvaccinated and at least 2 doses of mRNA vaccine (regardless of formulation), never COVID-19 vaccinated.

The full data available, from 01 December 2018, will be used as the look-back period to define patient's characteristics, clinical history, risk factors, and healthcare utilization.

TABLE 2. TARGET TRIAL AND TARGET TRIAL EMULATION

Target Trial Specification ^{16,17}	Target Trial Emulation			
Eligibility criteria				

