Inclusion criteria in trials generally reflected age-related eligibility for vaccination.	For brevity, we will not discuss each of the 5 aim's different inclusion criteria here. Throughout, we used age at time vaccine was authorized or approved by FDA for time-varying exposures, age at vaccination for time-fixed exposures to reflect age-related eligibility.			
	We require continuous pharmacy and medical enrollment in HealthVerity prior to index date (FDA EUA date per vaccine) for follow-up. This is in order to establish pre-existing health status, which would have been queried at study entry in the clinical trials.			
	We require continuous California/Louisiana residency to maximize pre-index capture of vaccines, as people living outside of California /Louisiana would not have prior vaccines well captured in the registry.			
	Throughout, we will exclude people who are currently pregnant, using a validated			

- Exclusion criteria
 - Pregnant
 - Treatment with immunosuppressive therapy or diagnosis with an immunocompromising condition
 - History of COVID-19

gestational age algorithm with up to 9 months lookback. 18

Except in aim 4, where the analyses are specific to immunocompromised persons, we will exclude immunocompromised people considering claims for medications dispensed as well as and diagnosis codes.

We will exclude persons with a diagnosis of COVID-19 in any setting ≤ 90 days prior to index. We are limiting to 90 days as reinfections have become more common over the pandemic and were rare during the Fall 2020 clinical trial period. We believe 90 days represents a reasonable period in which persons then can be considered to be at risk for reinfection, and also are eligible for vaccination. ¹⁹

We will exclude individuals with discrepancies in sex and/or year of birth between HealthVerity claims and California/Louisiana immunization registry datasets, as these are key confounders in all analyses. Secondary deidentified data makes it impossible to reconcile differences, which would be expected to be resolved with primary data collection.

Treatment strategies

Receive 1 dose of a BNT162b2 adapted formulation vs. no BNT162b2 formulation or other COVID-19 vaccine (XBB.1.5 or BA.4/5 depending on timing)

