5. RESEARCH METHODS

5.1. Study Design

This will be a retrospective cohort study using data from patients who were California or Louisiana residents in the HealthVerity claims database.

Cohort identification will begin from the date of Emergency Use Authorization (EUA) or U.S Food and Drug Administration (FDA) approval for the BNT162b2 formulation. Study follow-up will occur from FDA EUA or approval date until COVID-19 diagnosis or other outcome of interest (hospitalization, emergency department visit, outpatient encounter, end of medical and/or pharmacy enrollment, or death [according to the mortality database]).

The authorization/approval dates for each BNT162b2 formulation that will be used in this study are provided in Table 5.1.

Table 5.1 Timeline of Key BNT162b2 Regulatory Milestones Applicable to Pediatrics

Vaccine formulation	Age group	Event
BNT162b2 monovalent	Age 12 and	September 11, 2023: U.S. Food and Drug
XBB.1.5 COVID-19 vaccine	older	Administration (FDA) approval
	Age 6 months to 11 years	September 11, 2023: FDA emergency use authorization (EUA)
BNT162b2 bivalent BA.4/5 COVID-19 vaccine	Age 12 and older	August 31, 2022: FDA EUA
	Age 5 to 11	October 12, 2022: FDA EUA
	Age 6 months to 4 years	December 8, 2022: FDA EUA

All persons will be considered unvaccinated from date of FDA date of vaccine authorization/approval until, where applicable, 13 days after receipt of vaccine. In order to allow for time after dose for meaningful immunologic protection to accrue, persons will be considered vaccinated 14 days after vaccination.

The following data are available, from 01 December 2018, with varying look-back periods as outlined below to define patient's characteristics, clinical history, risk factors, and healthcare utilization.

The outcomes of interest are medically attended COVID-19, non-COVID-19 respiratory infections, mortality and healthcare resource utilization and are described in Table 5.2.

Main summary measure: VE = (1 - adjusted hazard ratio [aHR]) * 100, comparing vaccinated to unvaccinated persons

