Variable	Role(s)	Operational definition		
Influenza vaccination in 6 months prior to index	-Descriptive -Covariate	Assessed in 6 months prior to index Yes or No The list of codes is provided in the Protocol Annex		
Pneumococcal vaccination using all-available time prior to index	-Descriptive -Covariate	Assessed using all-available lookback data Yes or No The list of codes is provided in the Protocol Annex		
Herpes zoster vaccination using all-available time prior to index	-Descriptive -Covariate	Assessed using all-available lookback data Yes or No The list of codes is provided in the Protocol Annex		
Outpatient visits prior to index	-Descriptive (continuous and categorical) -Covariate (categorical)	Number of outpatient visits in 180 days prior to index Categorized as: 0, 1 or 2+ The list of codes is provided in the Protocol Annex		
Inpatient admissions prior to index	-Descriptive (continuous and categorical) -Covariate (categorical)	Number of inpatient admissions in 180 days prior to index Categorized as: 0, 1 or 2+ The list of codes is provided in the Protocol Annex		
Emergency department visits prior to index	-Descriptive (continuous and categorical) -Covariate (categorical)	Number of emergency department visits in 180 days prior to index Categorized as: 0, 1 or 2+ The list of codes is provided in the Protocol Annex		
Telehealth visits prior to index	-Descriptive (continuous and categorical) -Covariate (categorical)	Number of telehealth encounters (CPT: 99201-99215) in 180 days prior to index Categorized as: 0, 1 or 2+		
Number of documented SARS-CoV-2 tests in the 180 days prior to index	-Descriptive (continuous and categorical) -Covariate (categorical)	Number of visits in any setting with CPT in 180 days prior to index: 86408, 86409, 0225U, 0226U Categorized as: 0, 1 or 2+		
Prior post- COVID-19 conditions	-Descriptive -Covariate	Assessed using all-available lookback data, any encounter regardless of setting with ICD- 10-CM U09.9 "Post-COVID-19 condition" Yes or No		

Variable	Role(s)	Operational definition
Prior COVID-19 diagnosis	-Descriptive -Covariate	Any encounter with ICD-10-CM code: U07.1 between 90 and 365 days prior to index Yes or No
Prior bivalent BA.4/5 COVID-19 vaccine	-Descriptive -Subgroup	Where the BNT162b2 XBB.1.5 vaccine is the exposure of interest. Using all-available lookback data, received bivalent BA.4/5 COVID-19 vaccine (regardless of brand) prior to index Yes or No The list of codes is provided in the Protocol Annex

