5. RESEARCH METHODS

5.1. Study Design

This will be a retrospective cohort study using data from patients who were California or Louisiana residents in the HealthVerity claims database.

Cohort identification will begin from the date of Emergency Use Authorization (EUA) or U.S. Food and Drug Administration (FDA) approval for the BNT162b2 formulation. Study follow-up will occur from FDA EUA or approval date until COVID-19 diagnosis or other outcome of interest (hospitalization, emergency department visit, outpatient encounter, end of medical and/or pharmacy enrollment, or death [according to the mortality database]).

The authorization/approval dates for each BNT162b2 formulation that will be used in this study are provided in Table 5.1. Note that EUA (for children age 6 months to 11 years) and approval (age 12+) status for the bivalent vaccine was revoked on the date the XBB.1.5 formulation became available.

Table 5.1 Timeline of Key BNT162b2 Regulatory Milestones Applicable to Non-immunocompromised Adults

Vaccine formulation	Age group	Event
BNT162b2 monovalent	Age 12 and	September 11, 2023: U.S. Food and Drug
XBB.1.5 COVID-19 vaccine	older	Administration (FDA) approval
BNT162b2 bivalent BA.4/5	Age 12 and	August 31, 2022: FDA EUA
COVID-19 vaccine	older	-

All persons will be considered unvaccinated from date of FDA date of vaccine authorization/approval until, where applicable, 13 days after receipt of vaccine. In order to allow for time after dose for meaningful immunologic protection to accrue, persons will be considered vaccinated 14 days after vaccination.

The full data available, from December 1, 2018, will be used as the look-back period to define patient's characteristics, clinical history, risk factors, and healthcare utilization.

The outcomes of interest are medically attended COVID-19, mortality and healthcare resource utilization and are described in Table 5.2.

Main summary measure: VE = (1 - adjusted hazard ratio [aHR]) * 100, comparing vaccinated to unvaccinated persons during the same time period.

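### The Aim 1 and Aim 2 models count a prior COVID-19 diagnosis only if coded 90 to 365 days before index, so persons with only older codes are modelled as undiagnosed, which may confound VE

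*SAP*

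**What the plan says.** - **The covariate.** Aim 1 SAP Table 5.3 takes prior COVID-19 diagnosis as U07.1 "between 90 and 365 days prior to index", Yes or No. Aim 2 SAP Table 5.3 is the same: "Any encounter with ICD-10-CM code: U07.1 between 90 and 365 days prior to index". Section 5.7.5 of each SAP enters the Table 5.3 covariates in the adjusted Cox model as time-fixed terms.
- **Recent infection.** This is handled by exclusion. Protocol Table 2 states: "We will exclude persons with a diagnosis of COVID-19 in any setting ≤ 90 days prior to index". The target trial in the same table excludes any history of COVID-19, so the emulation leaves infection older than 90 days to adjustment.
- **Lookback, general statements.** Protocol section 8: "The full data available, from 01 December 2018, will be used as the look-back period". Aim 1 SAP section 5.1: "The full data available, from December 1, 2018, will be used as the look-back period to define patient's characteristics, clinical history". Aim 2 SAP section 5.1 is looser: "The following data are available, from 01 December 2018, with varying look-back periods as outlined below".
- **Lookback, operative rule.** Section 5.7.3 of both SAPs refers the reader to Table 5.3 for each covariate's baseline period.
- **The other COVID-19 history covariate.** Post-COVID-19 condition (U09.9) is "Assessed using all-available lookback data, any encounter regardless of setting" in Aim 2, but is limited to the year before index in Aim 1.
- **Required enrollment.** One year before index in Aim 1 and six months in Aim 2, each with a gap of up to 30 days allowed (section 5.2.1).

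**The concern.** A previous U07.1 code is the baseline history of the primary outcome itself. It may lower later risk through immunity, or mark a person who attends and gets coded. It may also influence whether that person takes the XBB.1.5 dose. A person coded only in, say, early 2022 is put in the same category as someone never diagnosed, and no reason is given for stopping at 365 days.

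Little else in the plan would cover the gap. Prior COVID-19 vaccination variables have descriptive and subgroup roles in Table 5.3, not a covariate role. The example negative controls (injury, ingrown toenail, atopic dermatitis) would not be expected to detect confounding by infection-acquired immunity. The named sensitivity analyses (7-day exposure definition, 3-month follow-up) do not address it. If the confounding is present, the headline VE and the subgroup VEs by prior vaccination would carry a bias that the confidence interval does not show.

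**Working it through.** **1. The window in dates.** Index is 11 September 2023.
- 365 days earlier is 11 September 2022 and 90 days earlier is 13 June 2023: 276 days counted inclusively. Day 90 itself also falls under the exclusion, so 275 days are effective.
- Data are held from 1 December 2018, which is 1,745 days before index. Of these, 1,745 − 365 = 1,380 lie before the window.
- Of those 1,380 days, 639 fall on or after 11 December 2020, the first EUA date in protocol Table 1.

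These are counts of days. The documents do not say how many coded infections fall in each period.

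**2. Benchmark for precision.** The plan states no figure for this covariate, so the comparison is with Aim 1 Table 5.4 (N = 9,000,000 × 0.95 = 8,550,000).
- I recomputed VE 30%, 1,000 cases per 100,000, with vaccination uniform from day 14 to day 182, exponential event times and 5% censoring. This gives 81,845 events at 9.6% uptake (16% × 60%) or 81,121 at 16%. The table states 81,108.
- The recomputed 95% CI is 27.2 to 32.7 or 27.8 to 32.2; the table states 28 to 32. The table is reproduced closely enough to serve as a yardstick.

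Half-widths read from the two Table 5.4s at VE 30%, as (upper − lower)/2:

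| Cases per 100,000 | Aim 1, 8.55 million | Aim 2, 3 million |
|---|---|---|
| 50 | (40−20)/2 = 10 | (45−11)/2 = 17 |
| 100 | (36−22)/2 = 7 | (41−17)/2 = 12 |
| 1,000 | (32−28)/2 = 2 | (34−26)/2 = 4 |
| 10,000 | (31−29)/2 = 1 | (31−29)/2 = 1 |

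**3. Possible shift in VE.** Let p1 and p0 be the shares of vaccinated and unvaccinated person-time with an older, unadjusted infection, and h the hazard ratio for the outcome given such an infection. The documents give none of these, so all are assumptions. The bias factor on the HR is

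B = (1 − p1(1 − h)) / (1 − p0(1 − h)), and observed VE = 1 − (1 − VE) × B.

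At true VE 30%:

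| p0 | p1 | h | B | Observed VE | Shift (points) |
|---|---|---|---|---|---|
| 20% | 12% | 0.7 | 0.964/0.940 = 1.0255 | 28.2% | −1.8 |
| 20% | 12% | 1.2 | 1.024/1.040 = 0.9846 | 31.1% | +1.1 |
| 12% | 20% | 0.7 | 0.940/0.964 = 0.9751 | 31.7% | +1.7 |
| 10% | 6% | 0.7 | 0.982/0.970 = 1.0124 | 29.1% | −0.9 |

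With equal shares, B = 1 and the shift is zero. More extreme assumptions at true VE 20% with h = 0.5 widen the range. Shares of 30% unvaccinated and 20% vaccinated give B = 0.90/0.85 = 1.0588 and VE 15.3% (−4.7). Shares of 20% and 30% give B = 0.85/0.90 = 0.9444 and VE 24.4% (+4.4).

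The formula treats older infection as independent of the covariates already in the model. To the extent that those covariates absorb part of its effect, the shift would be smaller.

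**4. The text.** Aim 1 section 5.1 promises full lookback for clinical history, and Table 5.3 gives one year: a direct conflict, although section 5.7.3 indicates that the table governs. In Aim 2, section 5.1 allows varying windows, so there is no conflict. Aim 2 does, however, use all available lookback for the high-risk conditions, pneumococcal and zoster vaccination and U09.9, and a shorter window for U07.1.

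**The case against.** The strongest reply has four parts.

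- **Uniform lookback.** Aim 1 requires one year of enrollment, and nearly all its clinical covariates use one year, so everyone is observed for about the same time. Claims held back to 2018 are not held for every person. This is a fair reason for keeping a one-year term in Aim 1. It does not explain Aim 2, where 365 days already exceeds the six months required.
- **Table 5.3 governs.** Section 5.7.3 makes it the operative rule, so the conflict in Aim 1 could be settled by editing section 5.1 alone. That is right about the text, but it leaves the adjustment question open.
- **Existing adjustment.** The models include outpatient, inpatient, emergency and telehealth visits, documented tests, wellness visits and U09.9. These should absorb part of the care-seeking pathway. They are not designed to capture immunity from an older infection. The protocol also lists residual confounding as a limitation.
- **Cost of a longer lookback.** Older infections would be unevenly ascertained, the youngest children cannot have one more than 365 days old, and rare pediatric outcomes have few events to spend. This stands, and it argues for one added term and not a finely split history.

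Two stronger readings are tempting. One is that the plan ignores all earlier infections. It does not: U09.9 captures some, and a person with an old code and another inside the window is entered as Yes. The other is that VE is therefore confounded, with most of the recorded history discarded. The documents give no difference in older infection by vaccination status and no residual effect. The window's 276/1,745 = 16% is a share of days, not of infections.

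**Conclusion.** The point holds as a risk of confounding from an avoidably narrow covariate, in both aims, with a direct text conflict in Aim 1 only. Bias requires that older coded infection differ by XBB.1.5 vaccination status and still affect risk after a year. Neither the size nor the direction can be derived from the documents.

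Under the assumed inputs at true VE 30% (shares of 6 to 20%, HR 0.7 or 1.2), the shift is 0.9 to 1.8 points in either direction. For Aim 1 that is comparable to the random error for common outcomes. For Aim 2 it is comparable only at 10,000 per 100,000, and for rare outcomes in either aim it is minor. The point concerns bias in the common-outcome estimates, not power. It is worth correcting because the data are already held and the remedy is cheap, not because the estimates have been shown to be wrong.

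**What to change.** 1. In both Table 5.3s, keep the 90 to 365 day term and add a Yes/No term for U07.1 more than 365 days before index, from all available lookback. Split it further by time only where events allow under section 5.7.2.
2. Reconcile Aim 1 section 5.1 with Table 5.3, so that the stated lookback and the covariate windows agree.
3. Add a sensitivity analysis of the primary outcome in persons with longer continuous prior enrollment (for example 3 years or more), because older claims are not held for everyone.

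**Cost.** SAP wording, one more degree of freedom (five more events under the five-per-variable rule) and one sensitivity analysis. Older infections will be unevenly ascertained in the main analysis, and uncoded infections stay missed either way. For rare pediatric outcomes the new term may have to be collapsed, which section 5.3.3 already permits.
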